To protect against the increased anxiety that is experienced prior to MRI scanning, participants receive information beforehand about what to expect, discuss with staff the methods for remaining still and feeling comfortable in the scanner, and receive training in the Simulator, all of which help to increase their familiarity with the scanning environment. Staff members are also highly experienced in the scan environment and help participants feel more comfortable in the scanner; however, if the discomfort cannot be reduced to an appropriate level, participants are told that they can discontinue the procedure at any time without penalty. To protect against risks associated with feeling uncomfortable in the scanner, and noise associated with the scanner, we use audio and video inputs, which decrease the feelings of being in an enclosed space for many participants. All participants will also be provided with earplugs and headphones to protect their hearing. Participants receive instructions before scanning about communicating with staff and scan operators, which can be done either by a squeeze bulb attached to the participant's headphone cord, or by voice through a microphone mounted inside the scanner. All participants will be told during consent and prior to the scan session that they can discontinue the procedure at any time without penalty.

Protection against risks from mobile sensing (binge eating participants only):

Previous studies with wristband sensors have indicated that after a brief adjustment period, the majority of the participants adjusted to wearing the bands and did not find them to be intrusive or restraining. Although slight discomfort is possible from wearing the wrist sensors, Fitbit sensors have been used in over 600 studies. Therefore, we assess the severity of the discomfort and irritation of wearing the wrist sensors to be minimal. If irritation persists to a point where the participant no longer wishes to participate, any irritation is entirely reversible once the participant removes the wrist sensors.

While electrical devices do introduce the risk of electric shocks, the probability of a participant experiencing even minor electrical shocks is negligible. High impedance circuitry is used to limit current flow, even in the case of external events (e.g., through physical breaking of the sensor board or shorting of the battery leads). All sensors in the wristbands are commonly used in mobile phones and other activity monitors and pose minimal risk to participants. We expect that the wrist sensors, which have precedent of prior use in a research study or have otherwise been designed for everyday wear, will elicit similar acceptability among the participants in this study.

Regarding privacy concerns, participants' contact information will be linked to their study data via a code. The key to this code will be available only to the research staff at Stanford, and will be secured separately from the rest of the study data that is transmitted to Fitabase. Participants will be informed of their rights to terminate their participation in the study at any time. Participants will also be informed of their rights to remove the wrist sensors if they so choose, if they do not wish to be tracked. Participants will be given a summary of the incentive structure, and will be informed how their participation will affect their final incentive payment.

All personnel that will be present for the research activities will be essential personnel in the conduct of this research. All personnel who will interact with participants at Stanford are trained in human participants research. Moreover, all staff at Small Steps Labs LLC, which owns and operates Fitabase, will receive only coded data. No directly identifiable data will be provided to Small Steps Labs LLC staff, and the key linking participant codes to identifiers will not be shared under any circumstances.

Study participants will be informed that this research is conducted with the use of Fitabase and that coded data, which will not directly identify them, will be maintained in a database owned and operated by Small Steps Labs LLC.

Protection against risks from carbon monoxide monitor (smoking participants only): While slight discomfort may result from participants holding their breath and exhaling, these carbon monoxide monitors have been used in several previous studies. Most participants are able to provide readings without issue. Participants will be informed of their rights to terminate their participation in the

study at any time if they experience excessive discomfort related to holding their breath or exhaling.

To minimize the risk of any spread of illness from the use of the carbon monoxide monitors, participants will each be provided with their own CO monitor. The CO monitors will not be reused by subsequent participants who enroll in the studies.

Protection against risks from physical activity intervention (binge eating participants only): Participants will be encouraged to set physical activity goals in line with their current health and fitness status. Participants who have concerns about increasing their physical activity will be encouraged to contact a medical professional.

Protection against risks from smoking quit attempts (smoking participants only): While participants may experience psychological discomfort from making a smoking quit attempt, this discomfort is not beyond what participants would ordinarily encounter in daily life (e.g., cravings, disappointment from a lack of success). Laddr is designed to support participants through a smoking quit attempt. Participants experiencing psychological discomfort beyond that encountered in ordinary life will be withdrawn from the study and referred to the appropriate resources.

Protection against risks from electronic databases: To protect the privacy or confidentiality of participants' data stored in electronic databases, every effort will be made to safeguard the confidentiality of research records, using data files free of information enabling individual identification of participants, lock-and-key access to paper records, and computer data files maintained with encryption, password protection, and behind firewalls. We will remove individual identifying information from data representations so that security failures would not put individual privacy and confidentiality at risk. Individual identifying information will only be maintained in a separate encrypted database with passwords known only to the PIs and specific members of the research team.

Each of the following sources of data is explained in detail separately: (1) eligibility, baseline, and follow-up surveys; (2) baseline and follow-up tasks; (3) baseline and follow-up neuroimaging; (4) EMA and Laddr (mobile intervention); (5) mobile sensing of physical activity (binge eating participants only); and (6)

carbon monoxide monitor (smoking participants only).

(1) We plan for the eligibility, baseline, and follow-up survey batteries and resulting data to be available and coordinated through Stanford's Research Electronic Data Capture (REDCap) system. All eligibility, baseline, and follow-up survey data will be either acquired using REDCap forms or stored directly in REDCap upon acquisition.

(2) Baseline and follow-up task data will be acquired using The Experiment Factory, a platform for deploying behavioral experiments that our team created and implemented in Aim 1 of this project. All task data will be coded (i.e., a unique participant code will replace all other identifying information) and stored on the OAK storage system in Sherlock2, a supercomputing cluster at Stanford University. Only essential members of the research team will have access to a key linking each code to participant identifiers.

(3) Raw neuroimaging data will be stored on Flywheel, a state-of-the-art platform for storing neuroimaging data that reduces security risk. All raw imaging data will be promptly coded to eliminate privacy and confidentiality issues and stored on the OAK storage system in Sherlock2 alongside task and summary imaging data.

(4) All EMA and Laddr usage data provided by participants when using the web-based Laddr[®] intervention will be stored locally on the phone in an AES-256 encrypted database. Data are stored in a key-value store residing on AES-256 encrypted solid state drives (encrypted at rest). Data are sent to the server when the device is online over an encrypted connection using Secure Sockets Layer (SSL) over Hypertext Transfer Protocol Secure (HTTPS) and will not be accessible to anyone not affiliated with the research project. The server is located in a locked cabinet, in a card-key secured room, in a secure, monitored data center in Fremont, California. The server is behind multiple firewalls with intrusion detection systems in place. Security patches for system software are installed within days and most often within hours after their release. All data stored on this server will be coded by participant ID number.

Stanford research staff will use an application, developed by the

same team that developed Laddr, to initiate Laddr for each participant at the beginning of the participant's study period. Throughout the study the team will download password-protected raw data files from a website created by the Laddr developers to monitor EMA completion and Laddr usage. These files will also allow the study team to track compensation amounts for each participant. Exported data will be identified via participant code and stored on password-protected computers. We successfully used this application, file download process, and similar procedures in the prior Aim 2.

(5) (Binge eating participants only) Mobile sensing data will be used to infer physical activity among this sample. These data will first be aggregated from the wearable sensors and will be stored on the participants' smartphones. After participants configure the proper settings, aggregated wrist sensor data from the smartphone will be transmitted automatically to Fitabase, a data management platform designed specifically for Fitbit data. All study data will be sent via a Secure Sockets Layer (SSL) connection, which encrypts all transmitted data. Stanford research staff will link mobile sensing data to a participant code so that participant identifiers (except for a study-specific code) are not included in the participant's Fitbit.com account or Fitabase.

Data are stored and indexed in the Fitabase SQL Server database. These database servers are IP firewalled and whitelisted such that they refuse any connection from IP addresses not preprogrammed by Small Steps Labs LLC, which owns and operates Fitabase. Fitabase databases are stored on the Microsoft Azure platform, which uses geographically dispersed data centers that comply with industry standards, such as ISO/IEC 27001:2005, for security and reliability. Small Steps Labs LLC maintains snapshot archives of the databases, which are encrypted and password protected, for disaster recovery purposes.

Participants may also be asked to input their activity data directly into Laddr as part of tracking their goals and progress. Activity data in Laddr will then be protected and transferred based on the same methods detailed above in section 4 about Laddr.

(6) (Smoking participants only) The CO monitors connect directly to participants' smartphones via the headphone jack. The CO readings will be

stored locally on participants' smartphones in a mobile application designed for the CO reader. Participants will input their CO readings from the device app directly into Laddr. The CO data will then be protected and transferred based on the same methods detailed above in section 2 about Laddr.

At the PIs' discretion, with the approval of the relevant IRB, and while the study is ongoing, any coded data from this project may be shared with other research team members within the [name]/[name] SOBC research team, and any de-identified data (i.e., stripped of all codes or other information that could be linked back to an individual participant) from this project may be shared with other researchers outside of the [name]/[name] SOBC research team.

After completion of the study, a de-identified dataset (i.e., stripped of all codes or other information that could be linked back to an individual participant) will be generated and made available to the research community as a whole. Informed consent procedures will ensure that participants are aware that consenting to participate in the study means consenting to inclusion in this open dataset.

All information that is collected from the participants will be the minimum necessary, and de-identified to the maximum extent possible, to conduct the research. Study participants will be informed that research data collected about them will be stored at Stanford until they are no longer useful. It is estimated that the data will possibly be useful for 10 years, but the data may be useful and may continue to be retained indefinitely. Eligibility data from the screening questionnaires will be retained for those who participate but will be deleted at the end of study for those who screen out or choose not to participate. Data may be retained indefinitely for those who screen in and sign consent, regardless of further participation.

Potential Benefits of the Proposed Research to Human Subjects and Others

Participants may learn self-regulation skills through the Laddr mobile application, which may have a positive impact on their smoking (in the smoking sample) or binge eating behavior (in the binge eating sample). Additionally, the information to be gained from their participation may benefit others in the future.

Importance of the Knowledge to be Gained

The proposed activities are designed to identify valid and replicable assays of mechanisms of self-regulation across populations to inform an ontology of self-regulation that can ultimately inform the development/refinement of health behavior interventions of maximal efficacy and potency. Because the need to alter health-related behavior is ubiquitous across medicine, understanding the extent to which the principles of effective health behavior change, and the mechanisms by which they work, are similar or different across health conditions and settings is a critically important area of scientific inquiry. It may inform more efficient, cost-effective, and patient-centered care. This line of research may ultimately allow us to make great strides in crafting “precision medicine” approaches for a wide array of populations. Given the importance of the knowledge to be gained, the risks to the participants are reasonable, as the risks are minimal and plans for protection against these risks are in place.

Data and Safety Monitoring Plan

Consistent with best practices, the Principal Investigator ([name]) will oversee all data and safety monitoring functions (described above) to ensure the safety of participants in the proposed study and to ensure the validity and integrity of the data obtained in the study. The Principal Investigator will also regularly meet with the Project Manager, Research Assistants, and Co-Investigators to track study progress and review these monitoring procedures. The Principal Investigator will regularly oversee all aspects of the study, including participant recruitment, informed consent, data collection, data management, and data analysis procedures, as well as regularly assess the risk/benefit ratio associated with participation in the study.

The Principal Investigator will train all project staff to recognize and report any adverse event immediately to them. Adverse events involving human participants include, for example, physical injuries, worsened physical or mental health, suicidal ideation, panic attacks, and depression. Other adverse events may also include the inadvertent disclosure by research staff of confidential research information to other persons and/or to staff of criminal justice or government agencies.

In the event that such adverse events are reported to the Principal Investigator, he will immediately inform the Chairperson of the appropriate Institutional

Review Board, who will make a decision about whether the reported event is a Serious Adverse Event (SAE) that must be reported to the National Institute on Drug Abuse (NIDA). If the Principal Investigator determines that there is sufficient evidence of an adverse event to necessitate suspension of data collection, further IRB review, modification of the protocol, or other changes, the Principal Investigator will immediately discuss this recommendation with the Chairperson of the IRB and reach a determination of whether to suspend data collection or to stop the study from proceeding. Resumption shall be based on the concurrence of the Principal Investigator, the Chairperson of the IRB, and any other relevant parties. NIDA will receive a written report within three days of any such suspension and/or resumption of data collection.

The Principal Investigator will provide an annual summary report of all adverse events to the IRB as part of the annual review and to NIDA as part of the annual Progress Report. If no adverse events have occurred, the report will state, "No adverse events affecting human participants have occurred during this project year."

Protocol Updates

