We propose the sample sizes above to reach 50 participants in each sample with at least 10% EMA response percentage over the duration of the four-week study (at least 12/112 EMAs). We calculated the percentage of participants who completed at least 10% of their EMAs in Aim 2 at Dartmouth. We then estimated a target sample size to reach at least 50 participants in each sample with adequate EMA participation (at least 10% completion). The proposed sample sizes account for participants who sign consent but participate minimally, and the target sample sizes of 50 for each sample with at least 10% EMA completion were determined through power calculations in Aim 2.

Statistical Analysis Plan

To evaluate the degree to which changing self-regulation is associated with changes in medical regimen adherence (measured as daily smoking abstinence in smokers and daily physical activity in overweight/obese individuals with binge eating behavior), we will fit several multilevel models (e.g., linear mixed-effects models) in addition to an overall model examining mechanistic effects. Details are provided in the following text. At the momentary level, there two relationships to be examined to understand the role of self-regulation in behavior change: the relationship between context and self-regulation, and the relationship between

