self-regulation and medical regimen adherence. We will examine each relationship separately prior to examining the full mechanistic model. To examine whether context is associated with level of momentary self-regulation, we will fit several multilevel models with momentary context as a predictor of momentary self-regulation measure. In Aim 2, we have identified several challenging contexts associated with worse momentary self-regulation, and we will confirm these relationships in this treatment-seeking sample of participants. The multilevel models will include a random individual-level effect to account for the non-independence of repeated observations over the 28-day period within an individual. Additionally, the models will also include a fixed effect of time to account for changes in momentary self-regulation over the treatment period. We will also consider a random individual-level slope term if there is significant variability in this change over time between individuals. Such a change in self-regulation over time may be due to the cumulative effect of Laddr use over the treatment period. We will also test whether including an interaction between context and recent Laddr usage is significant indicating Laddr use affects the association between context and momentary self-regulation. These models will identify contextual factors associated with increased or decreased momentary self-regulation.

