The next model will examine the relationship between level of momentary self-regulation and daily medical regimen adherence. One model for each subscale of the momentary self-regulation will be fit. In each model, momentary self-regulation will be the predictor and daily medical regimen adherence (smoking abstinence for smokers and daily physical activity for overweight/obese participants with binge eating disorder) will be the outcome. These models will identify the influence of momentary self-regulation on medical regimen adherence. Together with the previous set of models, the components of a mechanistic effect of momentary self-regulation on medical regimen adherence will be estimated. If each relationship is significant, we will fit a full multi-level structural equation model to examine the indirect effect of momentary context on medical regimen adherence as well as the direct effect of context on medical regimen adherence, independent of momentary self-regulation. Bootstrapping will be used in estimating the indirect effect in the mediation model. Bootstrapping involves taking numerous pseudo-replicate samples from the dataset and using the variability in the statistic from sample to sample to construct an interval estimate conveying the direction, magnitude, and precision

of an indirect effect. This mediation model will allow us to estimate the impact of self-regulation as a mechanism for decreased medical regimen adherence in challenging contexts.

At the individual level, we wish to examine whether Laddr can influence momentary self-regulation in a positive direction and, in turn, increase medical regimen adherence. To test this hypothesis, we will examine both the effect of time in the study on momentary self-regulation via multilevel models (e.g. linear mixed-effects models) as well as the effect of various Laddr engagement metrics on momentary self-regulation. Since Laddr use is offered as an intervention during the 28-day intervention period, time in study serves as a proxy for the cumulative effect of Laddr use. Since individuals will differ in their use of Laddr during the course of the intervention period, we will also examine Laddr engagement metrics (e.g., guides read, goals tracked) in addition to time. If Laddr usage appears to influence momentary self-regulation in a positive direction, we will again fit a multi-level structural equation model to examine both the indirect and direct effects of Laddr use on medical regimen adherence.

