
Additionally, we will evaluate whether Laddr influences task behavior in our four tasks as well as fMRI activity and connectivity by comparing the pre and post scan results.

[Power and Sample Size Justification](#)

With 77 participants in each sample with up to 4 EMA responses per day for 28 days, the maximum number of observations in the momentary dataset is 8,624. However, EMA response rates are not expected to be 100%, and some participants may withdraw from the study. With 10% study drop-out and 75% EMA completion rate, the number of observations in a momentary dataset may be closer to 5,821. Even with this sample size, there will be adequate power to detect momentary relationships between contextual factors and momentary self-regulation. For example, with intraclass correlations ranging from 0.3 to 0.6, and prevalence of contexts of interest (e.g., recent exposure to smoking cue, easy food access) between 10% and 30%, there would be at least 80% power to detect differences in momentary self-regulation measures between context between 0.05-0.10 times an SD. These are small effect sizes. In the pilot data, the average SD of a momentary self-regulation measure was between 0.5 and 0.9, and the stated standardized effect sizes are equivalent to detectable mean differences

between contexts of 0.03-0.09 points on the momentary self-regulation subscales, which range from 1 to 5. Well-developed formulae for determining power to detect indirect effects within a multilevel structural equation model of intensively collected data do not exist. However, simulation studies of the bootstrap approach at the individual-level indicate that with a sample size of 71, an indirect effect with medium-sized component effects ($\beta = .39$) can be detected with 80% power.¹

¹Fritz MS, [name] DP. Required sample size to detect the mediated effect. *Psychol Sci* 2007. Mar; 18(3):233-239.

Protection of Human Participants

Potential Risks:

The potential risks associated with the data collected are low.

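### The context models name no random participant slope for context and no participant-robust standard error, so their tests are anti-conservative if context effects differ between people

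*Combined protocol and SAP*

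**What the plan says.** The Statistical Analysis Plan section sets out the models with context as predictor and momentary self-regulation as outcome. Their random structure is given as: "The multilevel models will include a random individual-level effect to account for the non-independence of repeated observations". This reads most naturally as a random intercept. A fixed effect of time is added, and then: "We will also consider a random individual-level slope term if there is significant variability in this change over time between individuals". That slope is for time, not context.

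The same models carry two further tasks. For the context associations found in Aim 2, "we will confirm these relationships in this treatment-seeking sample of participants". On moderation: "We will also test whether including an interaction between context and recent Laddr usage is significant". Their significance is also one of two conditions for the mediation analysis: "If each relationship is significant, we will fit a full multi-level structural equation model".

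The Power and Sample Size Justification section says that "there would be at least 80% power to detect differences in momentary self-regulation measures between context between 0.05-0.10 times an SD", and translates this into mean differences "between contexts of 0.03-0.09 points on the momentary self-regulation subscales". It lists the number of observations, the ICC and the context prevalence, but no between-person variation in the context effect.

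**The concern.** A random intercept handles the fact that some people have higher self-regulation than others. It does not handle the possibility that temptation or easy food access lowers self-regulation a lot in some people and hardly at all in others. If that happens, the average context effect is estimated from about 69 person-specific effects, and its variance includes the spread of those effects divided by 69. A model without a context slope leaves that term out. Its p-values are then too small and its intervals too narrow, including for contexts with a real average effect.

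Nothing else in the SAP fills the gap. The interaction of context with recent Laddr use is a fixed moderator and does not absorb unexplained differences between people. Bootstrapping is planned only for the indirect effect. At stake are the confirmation of the Aim 2 associations, the identification of harmful contexts, and one of the two conditions for fitting the mediation model.

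**Working it through.** **Inputs from the Power and Sample Size Justification section**
- Observations: 77 × 4 × 28 = 8,624; after 10% drop-out and 75% completion, 8,624 × 0.9 × 0.75 = 5,821 (N).
- Participants: n = 77 × 0.9 = 69.3.
- ICC 0.3 to 0.6; context prevalence p from 10% to 30%; power 80%.

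**Assumptions, not in the documents**
- Two-sided 5% tests.
- Between-person SD of the context effect, tau, varied from 0 to 0.3 outcome SD.

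**Step 1: reproduce the stated range.** With a random intercept and one context effect common to everyone, v0 = (1 − ICC) / (N·p·(1 − p)) and the detectable difference is (1.960 + 0.842) × √v0.
- ICC 0.6, p 0.3: v0 = 0.4 / (5,821 × 0.21) = 0.000327; difference 2.802 × 0.01809 = 0.0507 SD.
- ICC 0.3, p 0.1: v0 = 0.7 / (5,821 × 0.09) = 0.001336; difference 2.802 × 0.03655 = 0.1024 SD.

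This matches 0.05-0.10. The alternatives tried do not: one-sided 5% gives 0.045-0.091, 8,624 observations 0.042-0.084, ignoring the ICC 0.080-0.122, and a full design effect 0.41-0.87. The stated range is therefore the calculation for tau = 0.

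**Step 2: let the context effect vary.** The true variance is v = v0 + tau²/n. The planned test uses v0, so:
- type I error = 2 × (1 − Φ(1.96 / √(v/v0)));
- coverage of a nominal 95% interval = 1 minus that, whatever the true average effect;
- detectable difference with a valid standard error = 2.802 × √v.

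Example, tau 0.2, ICC 0.6, p 0.3: tau²/n = 0.04 / 69.3 = 0.000577; v = 0.000904; SE ratio √(0.000904 / 0.000327) = 1.66; type I error 24%; coverage 76%; detectable difference 0.084 SD.

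**Step 3: range over the four ICC and prevalence corners**

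| tau (SD) | Type I error | Coverage | Detectable difference (SD) |
|---|---|---|---|
| 0 | 5% | 95% | 0.051-0.102 |
| 0.06 | 5.4-6.9% | 93-95% | 0.055-0.104 |
| 0.1 | 6-10% | 90-94% | 0.061-0.108 |
| 0.2 | 10-24% | 76-90% | 0.084-0.123 |
| 0.3 | 16-38% | 62-84% | 0.113-0.144 |

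The worst error rates come from ICC 0.6 with prevalence 30%. Type I error reaches 10% at tau between 0.10 and 0.20, depending on the corner. In scale points (outcome SD 0.5 to 0.9), the largest detectable difference at tau 0.3 is 0.144 × 0.9 = 0.13 on the 1-5 scale.

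**Step 4: simulation check** (69 participants × 84 observations, 4,000 runs, zero average effect). At the mildest and worst corners, the random-intercept test rejected in 6.7% and 10.2% at tau 0.1, 10.3% and 23.9% at 0.2, and 17.0% and 36.0% at 0.3. Participant-clustered standard errors held 4.8-5.3% throughout. With unequal response counts at the worst corner, the random-intercept figures were 6.9% at tau 0.06 and 24.0% at 0.2.

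**Step 5: the condition for the mediation model, for a context with no average effect** (the two tests taken as independent, the second relationship tested at 5%).
- Second relationship also null: type I error × 0.05, so 0.25% becomes 0.3-0.5% at tau 0.1 and 0.8-1.9% at 0.3.
- Second relationship real, with 80% power assumed: type I error × 0.80, so 4% becomes 5-8% at tau 0.1, 8-19% at 0.2 and 13-30% at 0.3.

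**The case against.** The strongest objection is that tau appears nowhere in the documents. The result runs from negligible to serious, and the largest figures need tau of 0.2-0.3 at one corner. That stands: a reader might infer that these tests are known to be badly inflated, and the documents do not show this. They show a model whose validity depends on an unstated quantity that Aim 2 data might supply.

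A second tempting reading is that trouble begins at a slope SD of about 0.06. It does not. Near 0.063 the low end of the SD range stops rounding to 0.05, and near 0.069 the high end stops rounding to 0.10. On the points scale the stated range survives rounding until about 0.076. Error inflation has no threshold: it begins at any tau above 0 and is slight at 0.06.

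Third, someone might conclude that the trial is too small. The detectable effects stay small at every tau tried, so this is not supported.

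Fourth, the effect on the mediation step is limited. The condition decides only whether that model is fitted, and the indirect effect then gets its own bootstrap interval. Entry stays below 5% when both relationships are null. It can exceed 5% when the second is real, but the figures for that case rest on an assumed 80% power. One should not infer that the inflation is confined to the context side, nor that the second side is also inflated: the SAP names no random effects for the self-regulation-to-adherence models, and no claim is made about them here.

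Finally, naming one random effect does not exclude others, so this may be incomplete wording. If a context slope was intended, the plan should say so. The SAP already anticipates that people differ in their time trend; the same reasoning applies to the tested predictor.

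**Conclusion.** The concern holds. As written, the context models give anti-conservative tests and intervals that are too narrow whenever context effects differ between people. Over the plan's own ICC and prevalence ranges, type I error is 5.4-6.9% at slope SD 0.06, 6-10% at 0.1, 10-24% at 0.2 and 16-38% at 0.3. The stated detectable range is that of a context effect identical in every participant. These sizes rest on the assumed tau, two-sided 5% tests, and (in the formula) equal response counts and equal prevalence across people. The same omission applies to the model for context by recent Laddr use, but no figure is given there because the between-person spread of usage is not documented. The change should be made because it is cheap and protects a step described as confirmatory.

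**What to change.** In the Statistical Analysis Plan section, specify a random participant slope for context in the context models and in the models for context by recent Laddr use, and do not make it conditional on a significance test. State that participant-clustered robust standard errors will be used if the slope model does not converge, which can happen when the slope variance is close to zero. In the Power and Sample Size Justification section, state the significance level and sidedness, and give the detectable differences over a range of non-zero slope SD, informed by Aim 2 data if available.

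The cost is SAP wording and a revised power statement, with no new data or participants. The downside is somewhat wider intervals and a slightly less favourable stated range. If context effects turn out to be nearly the same in everyone, little is lost.
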